### **A.2. Patient Standard of Care**

All study participants will receive standard of care for post-operative bunionectomy pain control. A standard amount of pain medication will be prescribed to all study patients. Oxycodone 5 mg – acetaminophen 325 mg will be given to all patients. Patients may take 1-2 tablets every 4-6 hours as needed for pain. Patients will be excluded if he/she has a known allergy or contra-indication to oxycodone or acetaminophen. In the event, an enrolled patient experiences adverse reactions from the standard of care narcotic pain medication (oxycodone 5 mg – acetaminophen 325 mg), this medication will be discontinued and the surgeon may provide substitute medications as deemed necessary. Any deviations from the initially prescribed oxycodone 5 mg – acetaminophen 325 mg, will be recorded and converted to a common scale if necessary.

Monitored anesthesia care (IV sedation) will be provided to all patients during his/her surgery. The anesthesiologist may convert to other forms of anesthesia if he/she deems it is medically necessary during the course of the surgery. The type and amount of peri-operative opioids and anti-emetics given by the anesthesiologist will also be standardized. The peri-operative opioid used will be fentanyl. The fentanyl will be titrated by the anesthesiologist in standard fashion to maintain vital signs (HR and BP within 20 % of preoperative values, and respiratory rate between 10-20. The peri-operative anti-emetic used will be Zofran as that is standard of care for the BIDMC Department of Anesthesiology. The surgeon will also administer pre-operative local anesthetic consisting of 15-20 cc's of 0.5% bupivacaine plain.

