#### **A.4. Screening, Enrollment, and Post-operative Course**

##### *a. Screening, Informed Consent, and Randomization*

All subjects will be treated pre-operatively by his/her surgeon. Once the surgeon determines the patient will require a Kalish bunionectomy, he/she will review the patient's medical record to determine if the patient meets the study inclusion/exclusion criteria. If the investigator/surgeon determines that the patient meets study criteria, he/she will discuss the clinical trial with the patient. If the patient expresses interest in participating in the clinical trial, the investigator/surgeon and/or research fellow will complete a standard screening form to determine the patient's eligibility. All eligible patients will be given a copy of the informed consent form for review. A screening log will be maintained. If the patient has additional questions, he/she will be given the principal investigator's and research fellow's contact information.

On the day of the surgery (*Day 0*), the informed consent will be reviewed again with the patient by one of the investigators. If the patient decides he/she would like to enroll in this study, they will sign the informed consent form, and will be randomized in the pre-operative holding area to either ketorolac or placebo. The patient and surgeon will be blinded to which study drug he/she was randomized to. Baseline information will be recorded including baseline pain scores. Pain will be measured by both unidimensional and multidimensional instruments. This will include the McGill Pain Questionnaire-Short Form (MPQ-SF) and the visual analog scale (VAS). The VAS will be 10 cm in length with the end anchors, "no pain" and "worse possible pain".

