#### **A.6. Randomization and Blinding**

Eligible patients will be randomized in the pre-operative holding area to either ketorolac or placebo by stratified permuted block randomization. Stratification will be by number of forefoot procedures (isolated Kalish bunionectomy versus Kalish bunionectomy plus additional forefoot procedures) and by unilateral versus bilateral (total of four possible strata: 1. Unilateral + Isolated Kalish Bunionectomy; 2. Unilateral + Kalish Bunionectomy with additional forefoot procedures; 3. Bilateral + Isolated Kalish Bunionectomy on one side; 3. Bilateral + Kalish Bunionectomy with any additional forefoot procedures. Any correlated cases will be accounted for in the analysis and are not common at this institution (but will be stratified in the event they do occur to help ensure balance between the study groups).

Study group allocation will be controlled by research pharmacy with sequentially numbered opaque sealed envelopes. This communication will occur entirely between the surgeon and research pharmacy. Allocation of ketorolac or placebo will be recorded on a "Randomization/Treatment" log that will be stored in a secure location with both opened and unopened randomization envelopes.

Access to this secure location will be controlled and locked. A coded master list will be kept in a locked and secured cabinet.

Patients, surgeons, anesthesiologists, and any assessors will be blinded. Only research pharmacy will not be blinded. Both ketorolac and placebo capsules and bottles and intra-venous preparations will appear exactly the same and will be prepared by research pharmacy. Assessors will be collecting data on post-operative pain and radiographic unions and will not be made aware of the patient's randomization results. In the event of an emergency or where the subject safety may be at risk, research pharmacy will unblind any necessary individuals to properly care for patients. In this event, the details of revealing the assigned study drug must be recorded in the subject's source documents.

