### **B. Statistical Considerations**

#### **a. Sample Size Justification:**

In performing the required sample size calculations, the authors assumed that potential cluster effects may be evident as a function of the individual surgeon. Because of this likelihood of cluster effects, we estimate the power of the study for change in post-operative pain that assumes an intra-class correlation (ICC) of at least 0.08 to inflate sample size estimates. This assumes 80% power to detect differences between groups with a 0.05 two-sided significance. Previous literature reports that in comparisons of opioid alone versus ketorolac with opioid the mean difference was observed to be 1.8 on the VAS (16). The widely accepted minimum clinically significant pain relief has been reported to be 1.3 (17). Detection of a 1.3 absolute difference in change in pain relief between groups requires 40 patients per group; detection of a 1.8 difference requires 20 patients per group consisting of eight and four (surgeons) respectively, assuming clusters of 10 subjects each. These calculations use an extremely high ICC which maximizes its accuracy. Because of the unknown ICC influence, a sensitivity analysis was performed assuming a non-contributory ICC of 0.08 which required a total sample size of 20 subjects per arm using the smallest clinically significant difference to detect.

Based on these calculations the largest sample required is 80 subjects. In order to preserve statistical power in the face of drop-outs and patient contact difficulties, the total sample size will be inflated by 10% such that the final projected sample size will be 88 subjects, or 44 per arm.

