**Thus, the previously noted 88 total sample size (44 patients per treatment arm) was estimated to**

**be adequate to achieve study aims and goals.**

**b. Data Analysis**

**Outcomes and their Measurements**

*a. Primary Outcome*

All analyses will be calculated using Statistical Analysis Software (SAS, Worldwide Headquarters, Cary, NC) and will be based on the **intention-to-treat principle**.

The primary outcome of interest is pain measured on the second post-operative day, 48 hours ( $\pm 4$  hours) following surgery. This will allow the effects of anesthesia to subside following surgery. This will be well within the five day window in which the patient will be taking ketorolac post-operatively.

Pain will be measured by both unidimensional and multidimensional instruments. A blinded trained research fellow will contact patients by telephone and will administer the McGill Pain Questionnaire-Short Form (MPQ-SF) and instruct patients to fill out the visual analog scale (VAS). This will occur 48 hours ( $\pm 4$  hours) post-operatively. The VAS will be pre-printed in a diary that is given to the patient post-operatively. The VAS will be 10 cm in length with the end anchors, "no pain" and "worst pain possible". If patient compliance with the VAS is greater than 95%, then the VAS will be used for the primary analysis. As a back-up, the MPQ-SF will be utilized as the primary analysis. Regardless, sensitivity analyses will be conducted to verify the robustness of the results. The research fellow will also obtain the patient's post-operative pain medication consumption (including timing and dosages) and verbally confirm study protocol compliance during this telephone interview (Please refer to the variables collected section for full details; A telephone script is also included in this IRB application). Regression will be utilized to control for measured confounders, including timing of the telephone interview and last dose of post-operative pain medication. Standard regression model rules will be applied and a p-value  $\leq 0.05$  will be considered statistically significant in the final regression model.

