#### *b. Secondary Outcomes*

The proportion of rescue narcotics will be compared between the ketorolac and placebo groups. Narcotics will be converted to standard morphine equivalents for statistical comparison.

On day two, the research fellow will also ask patient's his/her Global Evaluation of Study Medication by telephone. The patient will be asked, "How would you rate the study medication you received to delay pain". The choices will be on a four point scale: 1=poor; 2=fair; 3=good; 4=excellent.

Adverse events will be obtained from a standard form included in the patient's study diary. The proportion of adverse events will be compared between the ketorolac and placebo groups.

Time to regular shoe gear will be compared between the two groups. This information will be assessed during the post-operative visits and recorded within the secure BIDMC online medical record for each patient. Level of post-operative activity will also be evaluated with the help of the functional recovery index. This is a validated instrument for post-operative patients which includes three main domains: 1. Pain and social activity; 2. Lower limb activity; 3. General physical activity.

Summary statistics will be analyzed and reported. Continuous data will be analyzed with a 2-sided student's t-test if normally distributed or a Wilcoxon Rank Sum test if it cannot be justified through the Central Limit Theorem. From this data, confidence limits will be obtained and a 2-sided p value of  $\leq 0.05$  from the Fisher Exact Test will be considered statistically significant. If there are significant confounders identified, multivariate regression or stratification may be required and utilized if necessary. Binary data points will be compared by chi square analysis. From this, 95% confidence intervals will be obtained as well as a p-value from the Fisher Exact Test. A compliers-only analysis will also be secondarily performed if necessary, with the notion that this part of the study may have confounders and will not be part of the randomized comparison. Table 1 of the study will detail subject ages, gender, comorbidities, and other baseline study demographics.

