#### **B4. POSSIBLE BENEFITS**

No benefit is guaranteed to the patient for the participation in this study.

The primary objectives of the Kalish procedure are to reduce pain and improve function. All surgical procedures, even if they are elective out-patient surgeries, are associated with post-operative pain. As care providers, surgeons seek to achieve these surgical objectives while minimizing the pain that their patients experience. COX-2 inhibitors were considered to be an alternative to traditional NSAIDs but their use have suffered substantial drop off given concerns over potentially life-threatening adverse events. Ketorolac is a nonselective NSAID, inexpensive and widely available. Prior literature demonstrates that NSAID use in the post-operative period may reduce overall pain experienced and the frequency of opioid use. This represents a possible benefit to patients. Many surgeons already use ketorolac as described in this protocol, while others have concerns about delay in bone healing. The proposed study would provide evidence that has the potential to impact the standard of care throughout the United States in podiatric and orthopedic communities.

For the medical community as a whole, regardless of the outcome, this study and subsequent publications will represent the first randomized control trial on this topic. The study design will test the hypothesis such that the results will provide strong evidence that will advance either the supportive or detracting arguments.

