## **B6. RECRUITMENT AND CONSENT PROCEDURES**

### **Recruitment**

Previous long-term large clinical trials, through several NIH grants, have been conducted at our center. We will have access to a dedicated clinical research room as well as experienced and qualified research assistants who have successfully participated in numerous clinical trials. In addition, our facility hosts a dedicated two-year podiatric reconstructive and research fellowship and a podiatric medicine and surgery-36 residency.

Patients will be recruited from a large tertiary care institution which has one major primary foot and ankle clinic with satellite podiatry offices scattered throughout a metropolitan area. The demographics of the satellite patients are similar to those seen at the primary center for elective cases including bunionectomies. There are over 12,900 annual visits at the primary clinic and over 10,000 annual visits at the satellite clinics.

Surgical cases at our institution were reviewed for volume over the past two years. Adequate numbers of surgical cases were identified in both financial years 2007 and 2008 with 6 participating surgeons. An additional two surgeons have joined the staff in 2009 and volume is expected to either remain stable or increase. All eight surgeons are either board certified or board eligible by the American Board of Podiatric Surgery in both Foot Surgery and Reconstructive Rearfoot and Ankle Surgery. All are well versed in the indications and technique associated with the Kalish bunionectomy procedure. Please note that the power calculation also takes into account the estimated differences between surgeons by cluster analysis. Final analysis will also assess for differences between surgeons and surgeon experience and control for this by regression analysis if necessary.

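### The primary 48-hour pain regression adjusts for last dose of pain medication, which follows randomisation and which ketorolac may change, so its treatment coefficient is not the intention-to-treat effect

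*Combined protocol and SAP*

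**What the plan says.** Section B3.B.b (Data Analysis, Primary Outcome) declares that all analyses follow intention to treat and sets pain at 48 hours (±4 hours) as the primary outcome. On the model it says: "Regression will be utilized to control for measured confounders, including timing of the telephone interview and last dose of post-operative pain medication". It adds that standard regression rules apply and that p ≤ 0.05 in the final regression model counts as significant. No primary comparison without these covariates is named; the t-test and Wilcoxon text appears only under Secondary Outcomes.

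Four other places bear on the last-dose covariate:

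- Sections A.5 and A.6 place randomisation in the pre-operative holding area, before any post-operative dose.
- A.2 (Patient Standard of Care), on oxycodone-acetaminophen: "Patients may take 1-2 tablets every 4-6 hours as needed for pain".
- B4 (Possible Benefits), on prior literature: "NSAID use in the post-operative period may reduce overall pain experienced and the frequency of opioid use".
- Secondary Outcomes: "The proportion of rescue narcotics will be compared between the ketorolac and placebo groups".

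**The concern.** A confounder in a randomised comparison would have to precede assignment. Last dose comes after it, responds to the pain being measured, and may be changed by the study drug. The plan also treats the same behaviour in two ways: as an effect of treatment (the secondary outcome) and as a nuisance to be adjusted away (the primary model).

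The phrase can mean the amount of the last dose or the time since it was taken. Both readings fail. If ketorolac reduces how often opioids are taken, it changes the gap since the last dose as well as the amount.

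The adjusted coefficient then describes pain at equal medication, or at equal time since medication. It would still be reported as intention-to-treat, and it could hide a real benefit or overstate one. Adjusting for the time of the call is not the objection: blinded staff set it within a ±4-hour window.

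**Working it through.** **Inputs from the documents.** Detectable difference 1.3 on the VAS, 40 per group, 80% power, two-sided 0.05, ICC 0.08 with clusters of 10, and 10% inflation to 88 (Sample Size Justification). Dosing interval 4-6 hours (A.2).

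**The plan's own figure.** No SD is stated, so 40 per group can only be solved backwards.
- Without clustering, the normal approximation gives SD = 1.3 × √(40/2) / (1.960 + 0.842) = 2.07. The t-based value is 2.05, used below.
- With the clustering inflation, 1 + (10 − 1) × 0.08 = 1.72 and SD = 2.05/√1.72 = 1.56.
- 80 × 1.10 = 88, as stated.

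**Assumed inputs (illustrative; none is in the documents).** Within-arm correlation ρ between the medication variable and pain: 0.3-0.5. Shift s in that variable due to ketorolac: 0.3-0.5 of its SD. 40 analysed per arm.

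**Formulae.** With the covariate scaled to SD 1, its within-arm slope is ρ × SD, so adjustment removes ρ × SD × s from the treatment effect:
- adjusted effect = 1.3 − ρ × SD × s; the bias is 0.3 × 0.3 = 0.09 SD to 0.5 × 0.5 = 0.25 SD
- SE = SD × √(1 − ρ²) × √(2/40) × √(1 + s²/4), multiplied by √1.72 where the inflation is kept

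**Worked ends of the range at SD 2.05.**
- Unadjusted: SE = 2.05 × 0.2236 = 0.458; 1.3/0.458 = 2.84; power 81%.
- ρ = s = 0.3: effect 1.3 − 0.09 × 2.05 = 1.12; SE 0.442; power 71%.
- ρ = s = 0.5: effect 1.3 − 0.25 × 2.05 = 0.79; SE 0.409; power 49%.

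| Setting | Unadjusted power | Adjusted effect | Adjusted power | Effect if the sign is opposite |
|---|---|---|---|---|
| SD 2.05 | 81% | 1.12-0.79 | 71%-49% | 1.48-1.81 |
| SD 1.56, patients independent | 96% | 1.16-0.91 | 93%-83% | 1.44-1.69 |
| SD 1.56, inflation kept in SE | 81% | 1.16-0.91 | 75%-60% | 1.44-1.69 |

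**Direction.** If patients in more pain take more medication, or take it more recently, the adjusted effect shrinks. If opioid relief wears off, so that a longer gap means more pain, and ketorolac lengthens the gap, the adjusted effect grows. A large-sample simulation (true effect −1.3, SD 2.0, shift −0.5 SD) gave −1.55 when opioid lowers pain and nothing else links the two. It gave −1.02 when pain-prone patients also use clearly more opioid, and −1.30 in a middle setting where the two biases cancel. The model without last dose returned about −1.3 throughout.

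**Equal 48-hour pain, but less medication on ketorolac.** The test statistic is displaced by ρs / [√(1 − ρ²) × √(2/40) × √(1 + s²/4)], which is 0.42 to 1.25. Two-sided rejection is 7% to 24% instead of 5%; the SD cancels. With the 1.72 inflation kept in the SE it is 6% to 16%.

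**Timing reading.** If the call falls at a random point in a dosing interval I, time since last dose has mean I/2 and variance I²/12. An assumed 15%-25% fewer doses lengthens the interval to I/(1 − 0.15) or I/(1 − 0.25). At I = 5 hours the mean goes from 2.5 to 2.9-3.3 hours, a shift of 0.28-0.49 pooled SD. The shift in SD units is the same at 4 or 6 hours, and is 0.24-0.42 SD if intervals vary between patients with a CV of 30%. A shift of the assumed order can therefore arise on timing alone.

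**The case against.** The strongest reply is that the text is open. Last dose is named as a candidate covariate, the regression rules might drop it, and sensitivity analyses are promised whatever happens. B4 says only that NSAIDs in general may reduce opioid use. If ketorolac does not shift last dose, the adjusted and unadjusted linear-model coefficients estimate the same quantity.

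The size is also unsupported by the documents, and small values are plausible. With correlation 0.1 and shift 0.1-0.3 at SD 2.05, 1.3 becomes only 1.28-1.24 and power is 80%-77%. With the opposite sign and the main assumed range, power rises to about 92%-99%.

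The 7%-24% rejection rate is not a type I error for an inert drug. If ketorolac changes neither pain nor medication use, the test keeps its size (5.1% in simulation). Equal pain on less opioid is a real drug effect; the adjusted test simply answers a different question.

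These points stand as limits on magnitude and direction. They do not rescue the model. Nothing confines the last-dose adjustment to a sensitivity analysis, and the promised sensitivity analyses are not specified. If selection rules decide whether the covariate stays, the primary estimand depends on the data.

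**Conclusion.** The concern holds, and it is structural. Followed as written, the primary model adjusts for a variable that arises after randomisation, responds to pain and may be changed by treatment, so its coefficient is not the effect of assignment on 48-hour pain. This is so on the amount and the timing readings alike.

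The size rests on assumptions and runs from near zero to about a quarter of an SD, in a direction that cannot be known beforehand. At the upper end of the assumed range, a true 1.3 is estimated as 0.79 or as 1.81 (SD 2.05). Because this is the trial's primary test, it must be fixed before unblinding.

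**What to change.** 1. Remove last dose of pain medication, and any other post-randomisation variable that treatment can affect, from the primary model.
2. Analyse opioid use as its own outcome, as Secondary Outcomes already provides. Label any medication-adjusted pain model exploratory, not intention-to-treat.
3. Fix the primary model before unblinding: 48-hour pain (VAS, or MPQ-SF if the back-up rule applies) on treatment, the baseline value of the same instrument and the two stratification factors. Baseline pain is already planned for collection (A.4.a: "Baseline information will be recorded including baseline pain scores"). The factors are in A.6: "Stratification will be by number of forefoot procedures", and unilateral versus bilateral surgery.
4. State how correlated bilateral cases, which A.6 says will be accounted for, and surgeon will be handled. On surgeon, B6 now says: "Final analysis will also assess for differences between surgeons and surgeon experience and control for this by regression analysis if necessary".
5. Align the sample-size wording, "we estimate the power of the study for change in post-operative pain", with the 48-hour score that is the primary outcome.

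Baseline adjustment is a precision gain, not part of the bias correction. Its variance factor is 1 − r², so at r = 0.2-0.5 it adds about 2-10 power points at SD 2.05, but only about 0.6-3 points at SD 1.56 with independent patients.

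The cost is wording in the analysis section. All variables are already collected, and the planned 88 patients do not change.

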Pain will be measured by both unidimensional and multidimensional instruments. The McGill Pain Questionnaire – Short Form (MPQ-SF), Visual Analog Scale (VAS), pain medication related information, and study protocol compliance information will be collected at this time. The research fellow will instruct patients on how to fill out the visual analog scale (VAS) in the study diary. The VAS will be pre-printed in a diary that is given to the patient post-operatively. The VAS will have the end anchors, “no pain” and “worst possible pain”. If patient compliance with the VAS is greater than 95%, then the VAS will be used for the primary analysis. As a back-up, the MPQ-SF will be utilized as the primary analysis.

*d. Week One:* Patients will be evaluated in the clinic by his/her surgeon and re-banded. Patient diaries will be collected, post-operative medications will be counted, and study compliance will be verified.

*e. Week Two:* Sutures will be removed if appropriate and the patient may begin to get the surgical site wet. A soft bunion splint will be given to maintain soft tissue correction and is worn with the post-operative shoe for one more week. Range-of-motion exercises will be initiated and patients can be weight bearing as tolerated.

*f. Weeks Three through Five:* Anteroposterior and lateral foot radiographs will be taken at week three  $\pm$  one week. If the surgeon determines there is satisfactory healing, the patient will be transitioned to a supportive soft-soled shoe to initiate a propulsive gait. Range-of-motion exercises will be continued. The soft removable bunion splint is worn at bedtime for another 1-2 weeks.

*g. Week Six  $\pm 1$  week:* Weight bearing anteroposterior and lateral foot radiographs will be taken and the patient will be clinically assessed. If there is satisfactory healing, as determined by the surgeon, the patient can transition to normal activities. High impact activities, such as running or

jumping, will be avoided until the eighth week following surgery. Physical therapy will only be initiated if the surgeon determines its necessity. Indications for physical therapy may include a continued stiff joint or chronic edema.

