The patient diaries with the VAS will be collected during the first post-operative visit (one week). Patients will be asked to bring all surgery related medications and bottles to this post-operative appointment. The research fellow will again obtain the patient's post-operative pain medication consumption (including timing and dosages) by counting pills and verbally confirm study protocol compliance (Please refer to the variables collected section for full details).

Whether a difference in delayed unions at twelve weeks exists between the two groups will also be assessed. Radiographic union for each patient will be assessed by both a blinded, board-certified radiologist and two blinded board-certified podiatric surgeons. Agreement between these three experts will be assessed with a kappa score and the mean result will be used for primary analysis. Delayed and non-union rates will be compared between the two groups. A previously documented scoring system found to have both high inter- and intra-observer reliability in a series of tibial fractures reduced surgically will be utilized for this assessment. This scoring system grades each fracture according to four characteristics: 1. Rating of fracture healing, 2. Callus morphology, 3. Number of cortices visible or obliterated. 4. Number of cortices bridged (41). The modification utilized for this study will be as follows:

- ❖ **Grade 1:** Homogenous bone structure with complete obliteration of fusion site
- ❖ **Grade 2:** Massive bone trabeculae crossing fusion site, 3-4 cortices are bridged with fusion site barely discernable
- ❖ **Grade 3:** Apparent bone trabeculae crossing fusion site, 2-3 cortices are bridged with fusion site discernable
- ❖ **Grade 4:** Trace bone trabeculae crossing fusion site, 1-2 cortices are bridged with distinct visible joint space

- ❖ **Grade 5:** No bone trabeculae crossing fusion site, 0 cortices are bridged with complete visible joint space

A delayed-union will be defined as a grade 4 or 5 in any patient over twelve weeks. A nonunion will be defined as a grade 4 or 5 in any patient over six months. Analysis will include logistic regression for these binary endpoints. Odds ratios and 95% confidence intervals will be calculated between groups (delayed and/or non-union: yes/no). A 2-sided p value of  $\leq 0.05$  will be considered statistically significant.

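### Bone healing is compared between arms only as yes/no at twelve weeks and six months, with no ordinal analysis and no planned use of the week-3 and week-6 films, so a moderate delay would usually be missed

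*Combined protocol and SAP*

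**What the plan says.** Radiographic healing is a stated aim (B1, repeated under Figure 1). The clinical worry is about speed as well as failure: the Basic Science Overview raises delayed osseous healing, and B4 notes that some surgeons use ketorolac "while others have concerns about delay in bone healing".

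The Primary Outcome section of Data Analysis states the comparison: "Whether a difference in delayed unions at twelve weeks exists between the two groups will also be assessed". It sets out a five-level grade, read by one radiologist and two podiatric surgeons, all blinded. It then ties the grade to two cuts only: "A delayed-union will be defined as a grade 4 or 5 in any patient over twelve weeks" and "A nonunion will be defined as a grade 4 or 5 in any patient over six months". On method: "Analysis will include logistic regression for these binary endpoints", and "Odds ratios and 95% confidence intervals will be calculated between groups (delayed and/or non-union: yes/no").

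Section A.4 requires earlier films. "Anteroposterior and lateral foot radiographs will be taken at week three" (give or take a week), and weight-bearing films follow at week six. Their only described use is the treating surgeon's decision on progression. For week six: "If there is satisfactory healing, as determined by the surgeon, the patient can transition to normal activities". The plan does not say which visits the three blinded readers score. The secondary outcomes add time to regular shoe gear and a functional recovery index.

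**The concern.** Delay concerns when bone heals. A yes/no reading at week 12 records only who is still at grade 4 or 5 on that date. A patient whose union slips from week 6 to week 10 counts the same as one who did not slip. If few patients are at grade 4 or 5 by then, the comparison rests on a handful of events, and the information in grades 1 to 3 and in the earlier films goes unused.

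B4 says the trial will give strong evidence for one side of the bone-healing argument or the other. A non-significant week-12 result from a comparison with little power against moderate delay could be read as reassurance that it does not provide.

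**Working it through.** **Inputs.** About 40 evaluable per arm (80 before the 10% inflation to 88) and two-sided 0.05, from Sample Size Justification. No control rate for delayed union after a Kalish osteotomy is given. The nearest figure is 1/29 = 3.45%, the pilot nonunion rate. It comes from Lapidus patients who received ketorolac, so it serves here only as an illustrative low rate. Ketorolac rates, healing times and grade distributions below are all assumptions.

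**1. The plan's own figure.** The plan states 38 per arm for a 20.5-point difference at 80% power. With

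n = [1.96·√(2p̄(1−p̄)) + 0.8416·√(p₁(1−p₁) + p₂(1−p₂))]² / 0.205²

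n per arm is 34 at a control rate of 0%, 37 at 1%, 39 at 2%, 43 at 3.45%, 49 at 5.67% and 60 at 10%. So 38 corresponds to an unstated control rate of about 1–2%. At 40 per arm, 3.45% v 23.95% has 71% power by exact Fisher and 77% by normal approximation; 0% v 20.5% has 87% by normal approximation. The design can find an excess of that size.

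**2. A moderate week-12 excess, yes/no.** For 3.45% v 10% the expected counts are 40 × 0.0345 = 1.4 and 40 × 0.10 = 4.0. Fisher's test does not reject 0 v 5 of 40 (p = 0.055) and first rejects at 0 v 6 (p = 0.026). Summing over all tables:

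| Control v ketorolac | Fisher | Normal approximation |
|---|---|---|
| 3.45% v 10% | 7% | 21% |
| 5% v 10% | 4% | 13% |
| 5% v 15% | 18% | 32% |

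Pearson's chi-square, which is the score test of an unadjusted logistic model, has 23% power for the first row.

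**3. The same excess on the five grades at week 12.** Treat the grade as a cut-up normal variable. Moving 3.45% to 10% is a shift of 1.818 − 1.282 = 0.54 SD. Simulated Wilcoxon power at 40 per arm is:
- 57–59% with 20–50% of controls at grade 1
- 53% with 70% at grade 1
- about 45–47% with 80%
- about 40% with 85%
- about 33% with 90%

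This step isolates the loss from dichotomising. It says nothing about timing.

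**4. Timing.** Assume lognormal healing times, a control median of 6.5 weeks, and 3.45–10% of controls unhealed at week 12. Then σ = ln(12/6.5)/z = 0.613/1.818 = 0.337 at 3.45%, or 0.613/1.282 = 0.478 at 10%.

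- *1.25 times longer* (median 8.1 weeks): unhealed at week 12 on ketorolac is 1 − Φ(ln(12/8.125)/σ) = 12.4% or 20.8%. Fisher power is about 15–20% (exact enumeration 15% and 18%; simulation 16–20%). Chi-square gives 35% and 27%.
- *The same delay, week-6 grade by Wilcoxon*: the shift is ln(1.25)/σ = 0.66 or 0.47 SD, and power is about 47–73%. Evenly spread grades give about 48–78%. This assumes that the whole shift appears in the grade, with no reader error.
- *1.5 times longer* (median 9.75 weeks): 26.9% or 33.2% are unhealed at week 12, and Fisher power is 82% or 66%. Over control medians of 6–7 weeks the range is about 52–93%.
- *1.15 times longer*, medians 6–7 weeks: Fisher 2–10%, against 17–38% if the week-3, 6 and 12 films are combined as an ordered outcome. Neither is adequate.

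**The case against.** The trial defines delayed union by a twelve-week threshold and tests that definition; pain is the outcome named first. On that view an earlier or finer measure is a design preference, and nothing in the documents shows that the grade discriminates well at week 6. This stands as a reason to keep the planned endpoint and to label any addition supportive. It does not answer the loss of information at week 12 itself.

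The plan also has other measures. Time to regular shoe gear is related to healing, because the blinded surgeon's view of the film governs the change of shoe. It and the functional recovery index remain indirect. The six-month comparison tests failure to heal, and later films are taken only for those not united at week 12.

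The size of the gain depends on the test and the distributions. Logistic regression is planned, and the plan does not say which test goes with it. The Fisher figures are at the low end, and the ordinal advantage shrinks if nearly all controls are grade 1 at week 12.

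Four stronger readings are tempting, and the documents do not support them:
- *The early films are never graded.* The plan is silent on which visits are scored. It specifies no grading, which is different from ruling it out.
- *Most osteotomies are expected to have healed by week 6.* The milestones are conditional on satisfactory healing and no healing time is stated. The schedule supports, at most, an inference of healing before week 12.
- *A drug that slows healing by a few weeks would show no difference.* A delay of about three weeks on a 6.5-week median would be found more often than not.
- *Healing is compared only at twelve weeks.* Six-month nonunion is also compared.

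**Conclusion.** The concern holds for moderate delay. The plan's only between-arm radiographic comparisons are yes/no at twelve weeks and six months. They leave out most of a five-level grade and, as written, the week-3 and week-6 films. With 40 per arm, the week-12 comparison has about 7–23% power for 3.45% v 10%, against about 40–60% on the five grades. For healing 1.25 times longer it has about 15–20% by Fisher (27–35% by chi-square), against about 47–73% for the week-6 grade. Large effects, such as healing 1.5 times longer or a 20-point excess, would often be detected as planned.

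Every power figure rests on assumed rates, healing times and grade distributions. The direction is the same under both models; the exact size is not established. The point is worth acting on because the remedy is cheap, but it does not invalidate the planned endpoint.

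**What to change.** Leave the twelve-week and six-month yes/no comparisons as they are. Add to the Primary Outcome section, before unblinding, supportive between-arm comparisons of the 1–5 grade by a proportional-odds model or a Wilcoxon test:

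1. At week 12, using grades the readers already assign. This needs no extra reading.
2. At week 6, with the same three blinded readers grading the existing week-6 films in random order.

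State which visits are scored. State how three readings become one grade: the section uses a mean, which suits a Wilcoxon test but needs a rounding or median rule for a proportional-odds model. State how missing grades are handled, since counting lost patients as failures does not carry over directly to an ordinal scale. Report the effect with its 95% confidence interval, so that a null result shows what delay it leaves open.

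Cost: about 88 more film sets for each existing reader and one or two more bone-healing comparisons, reported as supportive. No visit, film, patient or clinical rule changes.
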